5.3. Methemoglobinemia Signs and Symptoms

The following 13 signs and symptoms that may be associated with methemoglobinemia will be collected. Decrease and/or resolution of these symptoms may be considered supportive of efficacy. This assessment is applicable only for the Primary case.

1. Grayish-blue skin discoloration
2. Cyanosis
3. Dyspnea
4. Headache
5. Fatigue
6. Weakness
7. Dizziness
8. Syncope
9. Coma
10. Seizures

11. Depressed CNS
12. Arrhythmias
13. Metabolic acidosis

Because the terms 'Grayish-blue skin discoloration' and 'Cyanosis' are essentially the same medically speaking, these 2 terms will be collapsed when the analysis dataset is created from the CRF database. If both boxes on the CRF are checked with identical time, the record with highest intensity grade will be flagged to be used for data summary; all records will be displayed in data listing.

Other noted signs and symptoms will also be collected (as 'Other'). Verbatim text of 'Other' signs and symptoms will be reviewed, and similar symptoms will be manually grouped into a group term when the analysis dataset is built. The grouped term will be labeled as the Modified term in the analysis dataset. Further, it is understood that some of these signs and symptoms may be inconsistently detected (such as cyanosis in a darkly pigmented patient) or inconsistently classified/severity-rated (such as "depressed CNS").

Data collection will include severity assessment per NCI-CTCAE grade and time of observations. In some incidences, a symptom could be reported without severity. Those incidences will be displayed as 'Y,' indicating that the symptom is present with unknown grade.

Observations from signs and symptoms assessments will be grouped into the following time periods:

- Before Treatment
- Posttreatment: \leq 24 hours
- Posttreatment: 24–48 hours
- Posttreatment: 48–72 hours
- Posttreatment: 72–96 hours
- Posttreatment: 96–120 hours
- Posttreatment: $>$ 120 hours

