6.1 Clinical Trials Experience

Because clinical trials are conducted under widely varying conditions, adverse reaction rates observed in the clinical trials of a drug cannot be directly compared to rates in the clinical trials of another drug and may not reflect the rates observed in practice.

The safety of PROVAYBLUE® was determined in 82 healthy adults of median age of 36 years (range, 19-55 years); 54% were male, and 68% were white. Each individual in the safety population received a single dose of PROVAYBLUE® 2 mg/kg intravenously. There was one serious adverse reaction reported (syncope due to sinus pauses of 3-14 seconds). The most common (>2%) moderate or severe adverse reactions were pain in the extremity (56%), headache (7%), feeling hot (6%), syncope (4%), back pain (2%), hyperhidrosis (2%) and nausea (2%). Table 1 lists the adverse reactions of any severity that occurred in at least 2% of individuals who received PROVAYBLUE®.

Table	1 Advorce	Pagetione	Following	Inflicion o	F DDAVAVDI	IIF® 2 ma/ka
12000	I Anverse	PIPMENNIS	6-4366436046646	ministra o	PRIMATE	THE Z HIMIZKO

Adverse Reaction		TEAE (n=82)	ng/kg Moderate-Severe TEAE (n=82)		
Pain in extremity	69	84%	46	56%	
Chromaturia	61	74%	0		
Dysgeusia	16	20%	1	1%	
Féeling hot	14	17%	5	6%	
Dizziness	13	16%		5%	
Hyperhidrosis	11	13%	ż	2%	
Vausea	11	13%	2	2%	
Skin discoloration	11	13%	4 2 2 0	2.70	
Headache	8	10%	6	7%	
Musculoskeletal pain	7	9%	Ö	1 10	
Paresthesia oral	7	9%	ŏ		
Paresthesia	7	9%	Ö		
nfusion site pain	5	6%	1	1%	
Feeling cold	5	6%	Ó	1 70	
Pallor	4	5%	Ö		
-alloi Dermatitis contact	4	5% 5%	0		
		5% 4%	0 3	4%	
Syncope	3		3 1		
nfluenza like illness	3	4%		1%	
Pruritus	3	4%	1	1%	
Anxiety	3 3 3 3 3 3	4%	0		
Decreased appetite	3	4%	0		
Chest discomfort	3	4%	0	001	
Back pain	2	2%	2	2%	
Cold sweat	2	2%	1	1%	
Dizziness postural	2	2%	1	1%	
Muscle spasms	2	2%	1	1%	
Presyncope	2	2%	1	1%	
Vomiting	2	2%	1	1%	
Arthralgia	2	2%	1	1%	
Chills	2	2%	0		
Diarrhea	2	2%	0		
Discomfort	2	2%	0		
Dyspnea	2	2%	0		
Erythema	2	2%	0		
-lypoesthesia oral	2	2%	0		
nfusion site discomfort	2	2%	Ŏ		
Limb discomfort	2	2%	Ŏ		
Oral discomfort	2	2%	Ö		
Catheter site pain	2 2 2 2 2 2 2 2 2 2 2 2 2 2 2 2 2 2 2 2	2%	ŏ		
Ecchymosis	2	2%	ŏ		

Other adverse reactions reported to occur following administration of methylene blue class products include the following:

Blood and lymphatic system disorders: hemolytic anemia, hemolysis, hyperbilirubinemia, methemoglobinemia

Cardiac disorders: palpitations, tachycardia

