Advise patients of the possibility of serotonin syndrome, especially with concomitant use of serotonergic agents such as medications to treat depression and migraines. Advise patients to seek immediate medical attention if the following symptoms occur after treatment with PROVAYBLUE®: changes in mental status, autonomic instability, or neuromuscular symptoms with or without gastrointestinal symptoms (see Warnings and Precautions (5.1)].

Advise pregnant women of the potential risk to the fetus with the use of PROVAYBLUE® during pregnancy [see Use in Specific populations (8.1)]. Breastfeeding

Advise patients to discontinue breast-feeding for up to 8 days after treatment with PROVAYBLUE® [see Use in Specific populations (8.2)].

Driving and Using Machines

Advise patients to avoid driving and use of machines during treatment with PROVAYBLUE®. Driving can be affected as a result of a confusional state, dizziness and possible eye disturbances [see Warnings and Precautions (5.6)].

Phototoxicity

Advise patients to take protective measures against exposure to light, because phototoxicity may occur after administration of methylene blue [see Adverse Reactions (6.1)

Skin and Body Fluid Blue Discoloration

Advise patients that PROVAYBLUE® may cause a blue discoloration of the skin and body fluids [see Adverse Reactions (6,1)].

Manufactured for: PROVEPHARM SAS [name]

Manufactured by: CENEXI [name]

Distributed by: American Regent Shirley, NY- 11967

Questions?: [name]

7/2017 28049163

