3.3. Endpoints

3.3.1. Efficacy Endpoints

The efficacy data summary will include the following endpoints:

- 1) Change from baseline in metHb after the first dose of ProvayBlue™ infusion.
The primary efficacy will be the number (%) patients with $\geq 50\%$ reduction in metHb based on the first available posttreatment assessment.
 - The following are secondary endpoints to support the primary endpoint.
 - i. Change in metHb posttreatment over time
 - ii. Time when 50% reduction in metHb is observed for the first time.
- 2) Change from baseline in vital signs (blood pressure, respiratory rate, and heart rate) after the first dose of ProvayBlue™ infusion.
 - The secondary efficacy will be the number (%) of patients with concomitant normalization of vital signs within 2 hours, inclusive, after the end of infusion of the first dose of ProvayBlue™
 - Time (hours) when the first incidence of normal vital signs was observed in patients who had abnormal baseline vital signs
- 3) In addition, 13 prespecified clinical signs and symptoms associated with methemoglobinemia and their intensity (as National Cancer Institute Common Terminology Criteria for Adverse Events [NCI-CTCAE] grade) before and after ProvayBlue™ treatment are collected. The presence/absence of those signs and symptoms will be treated as an 'other' efficacy endpoint since decrease and/or resolution of those signs and symptoms may be considered supportive of efficacy.

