5.3.1. Summary of Signs and Symptoms

Summary tables (Table 14.3.3.1.1, Table 14.3.3.1.2) will be prepared to provide number (%) of patients who had a given sign/symptom present. The percentage will be calculated using 2 different denominators:

- Reported: the denominator will be the number of patients who had assessment within each time period

[figure not shown]
- All Patients: the denominator will be the total number of patients in each patient group in the table.

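### The post-dose sign counts in SAP 5.3.1 do not separate persisting signs from new ones, so they can mix drug reactions with residual methemoglobinemia

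*SAP*

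**What the plan says.** SAP 5.3 opens: "The following 13 signs and symptoms that may be associated with methemoglobinemia will be collected". It adds: "Decrease and/or resolution of these symptoms may be considered supportive of efficacy". SAP 3.3.1 sets the rank: "The presence/absence of those signs and symptoms will be treated as an 'other' efficacy endpoint". That places the signs below the primary metHb endpoint and the secondary vital-sign endpoint.

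Two of the 13 signs are then merged: "Because the terms 'Grayish-blue skin discoloration' and 'Cyanosis' are essentially the same medically speaking, these 2 terms will be collapsed". Nothing limits the merge to pre-dose records. If both boxes are ticked for the same time, the record with the higher grade goes into the summary; both records stay in the listing.

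SAP 5.3.1 plans tables of the "number (%) of patients who had a given sign/symptom present", over one pre-treatment and six post-treatment periods, the first of which spans 24 hours. There are two denominators: patients assessed in the period, and all patients in the group. Neither is limited to patients who had the sign before treatment, and there is no rule on onset, worsening or cause.

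The label in Protocol Appendix 1 bears directly on this. Its patient counseling section says the drug "may cause a blue discoloration of the skin and body fluids". Its section 6.1 introduces the reaction rates: "Table 1 lists the adverse reactions of any severity that occurred in at least 2% of individuals who received" the drug, namely 82 healthy adults given a single 2 mg/kg dose.

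**The concern.** A count of patients with a sign present after dosing measures residual disease only if the sign has no other likely source. Here the drug itself is a listed source for several of the signs, and blue skin is the plainest case.

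A patient whose cyanosis has cleared but whose skin is stained, with the staining recorded as grayish-blue discoloration, would be counted under the merged skin term as still affected. A patient with no headache at baseline who develops one after infusion would add to the post-dose headache count. Either case makes symptom resolution look smaller than it was. The tables offer no way to see that this has happened.

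**Working it through.** **1. Overlap of terms.** After the merge, SAP 5.3 leaves 12 terms, which agrees with the 12 in SAP 5.3.2. Set against label section 6.1, Table 1 (denominator 82):

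| SAP term | Label count | Recomputed | Label states |
|---|---|---|---|
| Skin term (merged) | 11 (as skin discoloration) | 11/82 = 13.4% | 13% |
| Dizziness | 13 | 13/82 = 15.9% | 16% |
| Headache | 8 | 8/82 = 9.8% | 10% |
| Syncope | 3 | 3/82 = 3.7% | 4% |
| Dyspnea | 2 | 2/82 = 2.4% | 2% |

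The label's percentages reproduce. Five terms match directly. Coma and seizures appear in the label only as possible features of serotonin syndrome. For arrhythmias it has only related items (palpitations, tachycardia, one case of sinus pauses). Fatigue, weakness, depressed CNS and metabolic acidosis have no matching reaction. That accounts for 5 + 2 + 1 + 4 = 12.

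**2. What the table can show.** For one sign, let B be the patients with it before treatment, P those of B who still have it in a post-dose period, and N those in whom it is new. The table shows B and P + N. The apparent decrease is B − (P + N) = (B − P) − N. It falls short of true resolution, B − P, by exactly N, and N cannot be recovered from the table. Staining that replaces cleared cyanosis also raises P for the merged skin term.

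**3. Illustrative size for skin discoloration.** The documents give no rate at 1 mg/kg in patients, so the label rate is an assumption. Let p = 11/82 = 0.134 (exact 95% interval 6.9% to 22.7%). Expected patients = n × p; chance of at least one = 1 − (1 − p)^n. SAP section 1 gives 7 interventional and 24 observational patients, 31 in all. The efficacy set is limited to Primary cases with metHb before and after infusion. Its size is not given and cannot exceed 31.

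| n | Rate | Expected patients | Chance of at least one |
|---|---|---|---|
| 31 | label, 0.134 | 4.2 (2.1 to 7.0 over the interval) | 98.8% |
| 31 | half, 0.067 | 2.1 | 88% |
| 7 | label, 0.134 | 0.9 (0.5 to 1.6 over the interval) | 63% |
| 7 | half, 0.067 | 0.5 | 38% |

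The halving is a sensitivity value with no dose-response basis in the documents. All rows assume that every case of staining is entered on the symptom form.

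**The case against.** Several points on the other side are sound.

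- A reader might infer that the plan counts every listed post-dose sign as disease. It does not say so. SAP 5.3 says only that the signs may be associated with methemoglobinemia, and Protocol 12.2 asks after dosing for symptoms related to methemoglobinemia. Staining that the clinician recognises as dye should not reach that form. This stands for the 7 interventional patients. The other 24 come from a study that SAP 2.2.1 describes as largely passive chart review. The clinical-association question quoted there classifies cases and is not stated to apply to each post-dose record.
- The merge might be taken as the root cause. It is not: both skin terms were already on the list, so staining could be counted without it. The label speaks of skin discoloration and never of cyanosis. The merge makes matters worse by removing from the summary a distinction that Protocol Table 6-1 draws (grayish-blue discoloration at 3–15% metHb, cyanosis at 15–30%).
- The tables give presence, not a resolution rate. Individual figures plot grade against time and mark the first resolution, the listing holds all records, and narratives are the main presentation. This helps patient by patient but does not correct the summary counts.
- A reader might infer that drug reactions will be missing from the TEAE tables because SAP Table 3 puts signs and adverse events in separate domains. The documents do not support that. A storage domain does not exempt a sign from reporting: Protocol 15.3.1 and 15.3.3.1 require new, aggravated and worsening findings to be recorded as adverse events, and SAP 6.2 tabulates TEAEs by severity and relationship. What is absent is a stated cross-check between the two; SAP 6.2 verifies source only for patients with no adverse events.

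**Conclusion.** The concern holds in a limited form. As written, the post-dose counts can mix drug effects with residual methemoglobinemia for 5 of 12 terms, and the likely direction is against the drug, by understating symptom resolution. This is a risk in the planned summary, not a documented result.

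It touches only a descriptive, supportive endpoint. The primary metHb endpoint and the secondary vital-sign endpoint are unaffected, so nothing here supports a reading that the main efficacy conclusion is biased.

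For skin discoloration the size is about 4 patients if all 31 enrolled were in the efficacy set, about 2 at half the label rate, and under 1 of the 7 interventional patients at the point estimate. These figures assume that a 2 mg/kg healthy-adult rate carries over and that all staining is recorded as a disease sign. In so small a set, one or two patients visibly move a percentage, and the correction is cheap, so it is worth making.

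**What to change.** 1. In SAP 5.3, show grayish-blue discoloration and cyanosis as separate rows for post-dose records. This does not settle the cause of blue skin, but it keeps staining recorded under the first term out of the cyanosis row.
2. In the signs and symptoms summary table (14.3.3.1.1 and 14.3.3.1.2 in SAP 5.3.1, 14.2.3.1 in SAP 7.1; the numbering should be aligned), split post-dose signs into present at baseline and persisting, and new or of higher grade after the start of infusion. Report resolution only among patients who had the sign at baseline. Show records that cannot be placed because grade or time is missing as unclassifiable; SAP 5.3 and 5.3.2 acknowledge that both gaps occur.
3. Before database lock, compare new or worsened signs with the adverse event records and query the site where none matches. Do not convert them to TEAEs automatically. The sign data that SAP 5.3 describes cover grade and time, not relationship or seriousness, which the TEAE tables need. A new sign may also be rebound disease, which label section 5.3 describes with dapsone.

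The cost is SAP wording, some programming on data already collected, a few more table rows, some unclassifiable records, a short round of queries, and possibly slightly higher TEAE counts.

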5.3.1. Summary of Signs and Symptoms

Summary tables (Table 14.3.3.1.1, Table 14.3.3.1.2) will be prepared to provide number (%) of patients who had a given sign/symptom present. The percentage will be calculated using 2 different denominators:

- Reported: the denominator will be the number of patients who had assessment within each time period

[figure not shown]
- All Patients: the denominator will be the total number of patients in each patient group in the table.

5.3.2. Individual Profiles of Signs and Symptoms

Each symptom and its severity will be displayed via scatter bubble plots for each patient (Figure 14.3.3.2), showing the observed grade and relative time (X) to the first infusion. The first time when a symptom is judged to be resolved will also be displayed. Data with assessment time will be included in the graphic and all data (with and without time) will be included in the listing. This figure is illustrated in Figure 4.

All 12 prespecified signs and symptoms will be identified in the profile Y-axis, the sign/symptom NCI-CTCAE grade will be displayed if presented at a given time (X-axis). Any other symptoms will also be displayed using grouped term which will be reviewed and finalized based on verbatim term before database lock.

Figure 4: Example of Individual Profile of Methemoglobinemia Signs and Symptoms Before and After Treatment

6. SAFETY AND TOLERABILITY EVALUATIONS

Safety data summaries will be based on the safety analysis set. However, the data will be tabulated twice: the first table will include Primary cases only and the second table will include all patients. Safety data listing by individual patient will be prepared for all safety endpoints.

6.1. Total Exposure

Number of doses received and infusion duration will be tabulated (**Table 14.3.1.1** and **Table 14.3.1.2**). Please note that any patient without a recorded infusion stop time will have a missing infusion duration in this summary, although the missing infusion stop time is to be imputed in order to derive the relative time frame for efficacy endpoints (see [Section 3.3.2](#)).

6.2. Adverse Events

Adverse events reported after the first dose of ProvayBlue™ infusion start time and within 10 days after the last dose of ProvayBlue™ infusion will be considered treatment-emergent adverse events (TEAEs). Any AEs that do not have onset time will be included as TEAEs if reported. Patients who did not have any AEs will be verified via source documentation.

The Medical Dictionary for Regulatory Activities (Version 23) will be used to classify all AEs with respect to system organ class and preferred term. All adverse events will be listed.

The following summary tables will be produced for the TEAEs. All data summaries will provide number (%) patients as well as total number of events in each category by patient group. Each summary will be produced in 2 sets: one includes the Primary cases and one includes all patients in the safety analysis set.

1. a topline summary of TEAEs (**Table 14.3.2.1.1**, **Table 14.3.2.1.2**)
2. a summary table by preferred term in descending order of total incidence (**Table 14.3.2.2.1**, **Table 14.3.2.2.2**)
3. a summary table by system organ class and preferred term (**Table 14.3.2.3.1**, **Table 14.3.2.3.2**)
4. a detailed summary table by system organ class, preferred term and severity (**Table 14.3.2.4.1**, **Table 14.3.2.4.2**)
5. a detailed summary table by system organ class, preferred term and relationship (**Table 14.3.2.5.1**, **Table 14.3.2.5.2**)
6. a table of serious TEAEs by system organ class and preferred term (**Table 14.3.2.6.1**, **Table 14.3.2.6.2**)

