15.3. ADVERSE EVENT (AE) REPORTING

It is of the utmost importance that all staff involved in the study are familiar with the content of this section. It is the Investigator's responsibility to ensure compliance with reporting of AEs from his/her site.

Adverse events will be collected from the start of ProvayBlueTM treatment up to follow up 10 to 15 days after the last administration of ProvayBlueTM.

Any AE that occurs after the 10 to 15 days following the last administration of ProvayBlueTM which the Investigator assesses as related to a study procedure and/or ProvayBlueTM, should also be reported as an AE or a SAE.

All AEs should be followed until they are resolved or a clinically-stable endpoint is reached if they are considered chronic or until the patient is lost to follow-up.

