15.3.3.1. Adverse Event (AE) Reporting Period

ALL AEs or the worsening of any ongoing events which occur from PICD signature or the start of ProvayBlueTM treatment (whichever occurs sooner) up to 10 to 15 days after the last administration of ProvayBlueTM will be recorded in the CRF. All ongoing AEs and SAEs will be followed up until resolution, until the condition stabilizes, until the event is otherwise explained or until the patient is lost to follow up.

All AEs experienced by a patient, irrespective of the suspected causality, will be monitored until the event has resolved, any abnormal laboratory values have returned to baseline or stabilized at a level acceptable to the Investigator and Medical Monitor, until there is a satisfactory explanation for the changes observed, or until the patient is lost to follow-up.

Any untoward event that occurs after the AE reporting period but which the Investigator assesses as possibly related to ProvayBlueTM should also be reported as an AE or SAE.

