2.2.1. PVP-2016003

Protocol PVP-2016003 is an open-label, uncontrolled Phase 4 Interventional Study of patients who present in hospital/urgent care setting with acquired methemoglobinemia. The population may include pediatric and adult patients (males and females of all ages are included). Eligible patients will receive a single dose of study drug (typically 1 mg/kg of ProvayBlue™) treatment to treat acquired methemoglobinemia resulting in a direct health benefit. Patients will be followed post treatment; safety, efficacy, and PK data will be collected following a predefined data collection schedule (Table 2).

To create a harmonized electronic database, data collected from this study will be entered into the electronic data collection system used for the Observational Study, and the absolute dates of service recorded in this study will be converted to safe-harbor compliant “study days” before data are entered into the database for analyses. In instances where a specific procedure/data collection time was not initially recorded on the paper CRF, a data query will be generated to obtain the specific time from the site. All patients from this protocol are considered as Primary cases.

The original CRFs for Protocol PVP-2016003 requested posttreatment AE tracking, but the Study Procedure Chart indicates that AEs are tracked pretreatment. To be consistent with the Observational Study, any AEs collected prior to study drug treatment will be identified as NOT treatment-emergent events. Non-treatment-emergent AEs will be included in the data listing but will be excluded from data summary (see Section 6.2 for additional details).

Table 2: Study PVP-2016003 Procedures

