3.3.3. Safety Endpoints

The following safety endpoints will be summarized:

- Prevalence and nature of treatment-emergent adverse events (TEAEs), defined as all AEs with onset date after the first dose of ProvayBlue™ infusion and within 10 days of the last dose of ProvayBlue™ infusion.
- Results of clinical laboratory tests before and after ProvayBlue™ treatment.
- Results of ECG before and after ProvayBlue™ treatment.

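### Every AE table stops 10 days after the last dose, so later-onset events that PVP-2016003 collects up to its day 10–15 call would be listed but not tabulated

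*SAP*

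**What the plan says.** **What the interventional protocol collects.** Protocol 15.3 collects AEs from the start of treatment "up to follow up 10 to 15 days after the last administration of" ProvayBlue. Section 15.3.3.1 repeats that limit for the CRF: "up to 10 to 15 days after the last administration of" the drug. Events after that period which the investigator judges related "should also be reported as an AE or a SAE". Section 15.3.2 requires deaths to be reported over the same 10 to 15 days. The flow chart reproduced as SAP Table 2 gives the same end point in note s. Protocol 16.5 plans tables of all AEs by system organ class and preferred term, with no day limit.

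**What the SAP tabulates.** SAP 3.3.3 defines treatment-emergent AEs (TEAEs) as those with "onset date after the first dose of ProvayBlue™ infusion and within 10 days of the last dose". SAP 6.2 uses the same 10 days but attaches them to when the event is *reported*: "within 10 days after the last dose of" ProvayBlue. It then lists six AE summaries, including the serious-event one, all for TEAEs. Under SAP 2.2.1 (PVP-2016003), non-treatment-emergent AEs go into the listing but "will be excluded from data summary". SAP 4.1 fixes the status column of Table 14.1.1 at 10 days after treatment. SAP 7.1 contains no all-AE, non-TEAE or death table. SAP 7.2 does contain Listing 16.2.10 (all AEs) and Listing 16.2.15 (follow-up).

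**The other study.** SAP Table 1 gives the Observational Study an AE window of 10 days.

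**The concern.** Confirming safety and tolerability is a secondary objective of PVP-2016003, and that trial follows its patients beyond day 10. If the tables end at day 10 for everyone, the last part of its follow-up is observed but never summarised. A zero in the serious-event table would be a true statement about 10 days, yet a reader who knows the protocol could take it as covering the whole follow-up. The SAP does not mention the difference. The one consistency reason it gives, in 2.2.1 (PVP-2016003), concerns AEs before treatment, not the day-10 end.

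**Working it through.** The plan states no figure to reproduce. The check is a comparison of windows, followed by simple arithmetic on size.

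**Step 1. Trace an interventional patient's event through the planned outputs.**

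- *Dated AE or serious AE, onset after day 10.* Not a TEAE under SAP 3.3.3 or 6.2. It enters none of Tables 14.3.2.1.x to 14.3.2.6.x and appears in Listing 16.2.10.
- *Event with onset by day 10, death after day 10.* Protocol 15.3.2 treats death as the outcome of an event, so the event is recorded as fatal. By onset date it is a serious TEAE (Tables 14.3.2.6.x) and Grade 5 in the severity tables (14.3.2.4.x). Table 14.1.1 still shows the patient alive at 10 days.
- *Event with onset after day 10 that is fatal.* In no AE table, and not in Table 14.1.1 as a death. It appears in listings only, and probably in a narrative.
- *Onset by day 10, first reported at the call after day 10.* A TEAE under 3.3.3, but not under a literal reading of 6.2.
- *AE with no onset time.* Counted as a TEAE under 6.2, whenever it occurred.

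**Step 2. Length of the gap.** Inputs: SAP limit of 10 days; protocol call on day 10 to 15.

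- Call on day 10: 10 − 10 = 0 days.
- Call on day 15: 15 − 10 = 5 days, and 5/15 = 33% of that patient's collection period.

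The literal reading of 6.2 could add to this. The follow-up visit is on day 5 to 10, so an event starting after the visit and by day 10 may first be reported at the call. That is a further 10 − 10 = 0 to 10 − 5 = 5 days.

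**Step 3. Patients affected.** SAP 1 gives 7 interventional and 24 observational patients enrolled: 7/(7 + 24) = 7/31 = 22.6%.

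**Step 4. Effect of one untabulated event.** At most 1/7 = 14 percentage points in the trial alone, or 1/31 = 3 points in the pooled set. This assumes that all enrolled patients were treated and that the patient has no earlier event in the same table row. The 1/7 figure is for scale only, because the SAP plans no AE table by study.

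**Step 5. Chance that any such event occurs.** The documents give no late-event rate, so the per-patient risk p of an event with onset after day 10 and by day 15 is an assumption. The chance of at least one among 7 patients is 1 − (1 − p)^7:

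| Assumed p | Chance of at least one |
|---|---|
| 2% | 13% |
| 5% | 30% |
| 10% | 52% |
| 20% | 79% |

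This range shows only that the issue could arise. It does not estimate how likely it is.

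**The case against.** The strongest defence is that this is a plan for pooled data. Ten days is the only AE window the two studies share, so a common cut-off keeps the pooled tables comparable. SAP 1 also states that the SAP overrides the protocols' statistical sections, so protocol 16.5 does not bind. SAP 4 expects results mainly as individual narratives, and with 7 interventional patients the listings and narratives would show any late event.

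Most of this stands. The 10-day limit is sound for the pooled tables and should stay. What it does not explain is why the trial with longer follow-up has no table of its own over that follow-up. The precedence clause settles the conflict with protocol 16.5, but the collection period in protocol 15.3 is not part of a statistical section, and the SAP nowhere says that the later data will go untabulated.

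A reader might go further and infer that late safety data are discarded, or that every late death disappears from the AE tables. The documents support neither. All AEs are listed, and a fatal event with onset by day 10 remains a serious TEAE under 3.3.3. A reader might also cite the exclusion sentence in SAP 2.2.1 as aimed at late events. Its wording is general enough to reach them, but its paragraph is about events before treatment.

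**Conclusion.** The mismatch holds. A dated event with onset after day 10 in an interventional patient reaches no summary table, and a death after day 10 is missed by the disposition table. The 33% in step 2 should not be read as a third of the safety evidence: it is a maximum share of calendar days, not of events, and it falls to zero when the call is on day 10.

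The conclusion assumes that late events are recorded with an onset date and that all interventional patients were treated. It does not depend on any assumed event rate. This is an inexpensive improvement to reporting, not a defect that undermines the safety analysis. The disagreement between 3.3.3 and 6.2 on how events are dated needs settling in any case, because it decides whether some events that began within 10 days are counted.

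**What to change.** 1. Leave the 10-day pooled TEAE tables unchanged, including the serious-event Tables 14.3.2.6.x. Adding later events to those would mix two windows under a TEAE title and admit late events selectively.
2. Add one supplementary table for PVP-2016003 only, labelled with its own window: all AEs, serious AEs and deaths from first dose through the day 10–15 contact. Footnote in that table any later event judged related.
3. Make SAP 6.2 agree with 3.3.3 by dating events by onset, so that an event starting by day 10 but first reported at the call counts as a TEAE. Keep the existing rule for events without an onset time.
4. SAP 3.1 transfers only selected CRF elements to the pooled database. Confirm that interventional AE and death records after day 10 are among them.

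The cost is one small table on up to 7 patients, from data the protocol already requires in the CRF, and the need to label two windows clearly.
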